14.3. Samples storage

Plasma will be stored at all visits for confirmation tests (HCV genotyping, HCV sequencing, HCV resistance testing RAV, IL28B gene) as needed. The plasma samples will be centrally stored in laboratory of Institute for Medical Research, Kuala Lumpur, Malaysia for the Malaysian patients samples and in PHPT-AMS Laboratory for the Thailand patients samples up to 5 years, in order to allow regulators to inspect and control the data. Stored samples will not be used for future studies.

14.4. Shipment of samples

Full blood count, Liver function test, total bilirubin, ALT/ AST, serum Creatinine, fasting blood sugar, Coagulation, Urinalysis, anti-HCV, HBsAg, HIV, will be done in respective study sites' laboratories.

Urine pregnancy tests (dipstick) will be done on each site.

Samples for HCV RNA and HCV genotype will be sent to laboratories as described in the contact details section.

For Thailand, samples for HIV RNA and CD4 count will be performed at each site or will be shipped and analysed at the Associated Medical Science laboratory, Chiang Mai University.

For Malaysia, samples for HIV RNA and CD4 count will be shipped and analysed in Hospital Kuala Lumpur for stage 1 and to laboratories in Hospital Kuala Lumpur or in IMR for stage 2.

Pharmacokinetic samples will be stored at -80°C and shipped to the central laboratory on a regular basis on dry ice together with the sample log to PHPT-AMS Laboratory, Chiang Mai, Thailand.

Hair samples will be stored at room temperature, and not in a fridge and will be shipped on a regular basis to the central laboratory Service de Pharmacologie-Toxicologie, Faculté de Médecine PIFO, INSERM U-1173, Université Versailles Saint-Quentin, Garches at room temperature.

Stored plasma samples will be kept in laboratory of Institute for Medical Research, Kuala Lumpur, Malaysia for the Malaysian patients samples and in PHPT-AMS Laboratory for the Thailand patients samples

Stored plasma samples for HCV sequencing, HCV resistance testing RAV, IL28B gene will be shipped to and analysed by PHPT-AMS Laboratory, Chiang Mai, Thailand and/or at Laboratory of Virology in the Geneva University Hospital, Switzerland.

14.5. Laboratory analysis

All laboratory analysis will be performed in accordance to the laboratory manual derived from the individual institution.

15. Assessment of safety

- Incidence of premature discontinuation of treatment and premature discontinuation of study – for any reason, for non-compliance, and for safety-related reasons
- Incidence of adverse events, and laboratory abnormalities during the observation period, i.e. from signature of informed consent to 24 weeks after end of treatment;
- Incidence of serious adverse events from signature of informed consent to 24 weeks after end of treatment;
- Incidence of grade 3-4 clinical and laboratory Aes through 24 weeks after the end of treatment.

Subjects will be monitored for clinical and biological adverse events. These will be reported using DAIDS toxicity grading tables xi.

15.1. Adverse Events definitions

15.1.1. Adverse event (AE)

An adverse event is defined as any untoward medical occurrence (any 53nfavourable and unintended sign, symptom or disease, including an abnormal laboratory finding) in temporal association with the use of the investigational treatment and may or may not be causally related to it.

Definition of an AE includes worsening (in severity and frequency) of pre-existing conditions ("Medical history") before first administration of the investigational treatment and abnormalities of procedures (i.e. ECG, X-ray...) or laboratory results which are assessed as "clinically significant".

Abnormal laboratory (hematology and biochemistry) results will be reported as adverse events if the abnormality occurs or worsens after institution of the study treatment, and if the subject requires clinical intervention or further investigation, unless associated with an already-reported clinical event.

15.1.2. Surgical Procedures

Surgical procedures themselves are not Aes; they are therapeutic measures for conditions that require surgery. The condition for which the surgery is required may be an AE, if it occurs or is detected during the study period.

Xi http://rsc.tech-res.com/safetyandpharmacovigilance/gradingtables.aspx

15.1.3. Serious adverse event (SAE)

Any untoward medical occurrence (i.e. an adverse event) that meets at least one of the following criteria

- Results in death: i.e. causes or contributes to the death.
- Is life threatening
 In this context refers to an AE in which the patient was at risk of death at the time of the AE. It does not refer to an AE that hypothetically might have caused death if more severe
- Requires inpatient hospitalization or prolongation of an existing hospitalization

 i.e. the AE requires at least an overnight admission or prolongs a hospitalisation beyond the
 expected length of stay. Hospital admissions for a surgery planned before study entry, for social
 reasons for any elective surgery (i.e. plastic surgery) or for normal disease management
 (including treatment adjustment) are NOT to be considered as a SAE

 
- Results in persistent or significant incapacity or substantial disruption of the ability to conduct normal life functions,
 - i.e. the AE resulted in a substantial disruption of the ability to conduct normal life functions
- Results in a congenital anomaly/birth defect, or
 i.e. an AE outcome in a child or foetus of a subject exposed to the investigational Product before
 conception or during pregnancy.
- is an important medical events, i.e. is medically significant that may not result in death, be immediately life-threatening, or require hospitalization may be considered serious when, based upon appropriate medical judgment, they may jeopardize the patient or subject and may require medical or surgical intervention to prevent one of the outcomes listed in this definition. Any suspected transmission via a medicinal product of an infectious agent is also considered a serious adverse event.

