Adherence				Х	Х	Х	Х	Х				
Study Drug Dispensing			Х		Х	Х	Х					
PROQOL-HCV			Х			Х				Х		

¹ Eligibility and screening can be done on the same day for already HCV diagnosed subjects

² For subjects tested for the first time for HCV, extensive information and counselling perform HCV serology and confirm HCV chronic infection.

³ At screening a full clinical assessment is required and the signs or symptoms of hepatic decompensation must be documented. On other visits-a symptom directed assessment is required. In addition, for the cirrhotic group features of decompensation like ascites or hepatic encephalopathy need to be assessed and the CTP score calculated.

⁴ Fibroscan can be conducted at Screening visit or baseline FibroScan within 12 months to screening maybe use to assign treatment duration. A repeat FibroScan will be done at treatment W12 and W12 and W24 post treatment visits. A F broscan can also performed at all long term follow-up visits (until one year after end of treatment for patients cured and until 3 years after end of treatment for non-cured patients- see details of assessments in section 13.5.2).

⁵ CTP and coagulation tests are applicable to cirrhotic patients only and score based on the CTP score chart provided. Cirrhotic patients must continue their HCC surveillance program and any finding of HCC is suspected/confirmed to report as AE. A coagulation test can also performed at all long term follow-up visits (until one year after end of treatment for patients cured and until 3 years after end of treatment for non-cured patients- see details of assessments in section 13.5.2)

⁶ Urine pregnancy test to be done for women of child bearing age

⁷ For stage 1, HCV RNA will be performed on stored samples if SVR12 is not achieved or on any patient at any time if needed. For stage 2, HCV RNA will be performed on all samples on an ongoing basis at each treatment visit.

^{7a} Will be performed on stored samples for all patients

⁸ For HIV positive cases only (HIV monitoring (CD4 and viral load) is part of the standard of care for HIV subjects enrolled in the study. Closer follow-up performed upon clinical judgment of the principal investigator will be paid by the study).

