15.2. Adverse events reporting

15.2.1. Detecting and documenting AE

The investigator is required to report all directly observed Aes and all Aes reported by the trial subject using concise medical terminology. In addition, at each visit the subjects will be questioned about the occurrence of Aes, with a generic question such as "Since your last visit have you experienced any health problems?"

Stage 1 (for patients who did not consent for long-term follow-up visits): The AE reporting period for this stage of the trial begins upon subject enrolment in the trial (after signature of informed consent for treatment initiation) until 24 weeks' post-treatment completion.

Stage 1 (for patients who consented for long-term follow-up visits) and stage 2: The AE reporting period for this stage of the trial begins upon subject enrolment in the trial (after signature of informed consent for treatment initiation) until:

- End of long-term follow-up visits (SVR 24 + one additional visit for cured patients and 5 additional visits for virological failures): for all serious adverse events.
- End of long-term follow-up visits (SVR 24 + one additional visit for cured patients and 5 additional visits for virological failures): for all liver-related serious and non-serious adverse events.
- 24 weeks' post-treatment completion (SVR 24 visit): for adverse events not associated with any liver-related and not serious.

For both stages of the study:

Serious adverse events will be followed and reported until resolution or stable state.

Information on Aes must be evaluated by a physician. Each adverse event is to be classified by the investigator as serious or non-serious. This classification will determine the reporting procedure for

the event to DNDi and Regulatory Authorities/Ethics Committees (as per local regulatory requirements).

All patients who have Aes, whether considered associated with the use of the investigational product or not, must be monitored to determine the outcome. The clinical course of the AE will be followedup according to accepted standards of medical practice (i.e. until they are resolved or the investigator assesses them as chronic or stable or the subject participation in the trial ends (i.e., until a final report is completed for that subject), even after the end of the period of observation, until a satisfactory explanation is found or the Investigator considers it medically justifiable to terminate follow-up.

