15.2.2. Adverse Event reporting processes

Initial SAE reports will be reported to EAE Group if they meet the following minimal criteria:

- a. An identifiable patient
- b. A suspect medicinal product (at least one)
- c. An identifiable reporting source
- d. An event or outcome that can be identified as serious and unexpected Causality assessment will be reported asap.

All serious adverse events must be reported in an expedited manner to DNDi through [contact], whether or not the event is considered medication-related (within **24 hours of awareness of SAE** by the investigator), using the SAE (EAE) report form. This includes a description of the event, onset date and type, duration, severity, relationship to each study drug, outcome, actions taken, and all other relevant clinical and laboratory data.

Event	Time Frame	How to report	Report to
AE	NA (same time frame	AE CRF	Data Management
	as other CRF forms)		Center
SAE	24 hours	AE CRF + EAE (at least	DNDi EAE Group; Data
		email notification shortly	Management Center
		followed by EAE form)	_
Pregnancy*	72 hours	Pregnancy surveillance	DNDi EAE Group; Data
		form	Management Center
Spontaneous Abortion	24 hours	EAE (EAE form) +	DNDi EAE Group; Data
-		Pregnancy surveillance	Management Center
		form	-
Other Pregnancy Outcome	72 hours	Pregnancy surveillance	DNDi EAE Group; Data
incl. birth		form and Child	Management Center
		surveillance form	-

*if pregnancy leads in a reportable SAE, EAE form is to also be used and reported within 24 hours

The initial SAE report is to be followed by submission of additional information (follow-up SAE form and any other relevant source documents) as they become available.

Any follow-up report should be submitted as soon as possible, preferably within 5 working days.

Timelines for regulatory reporting in Malaysia (NPRA) and Thailand (Thai FDA):

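### The SAE exemption for disease-management admissions is not limited to planned or deterioration-free admissions and is not reconciled with the AE definition

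*Protocol*

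**What the plan says.** Section 15.1.3 lists the criteria that make an AE serious; one is enough. The hospitalisation criterion reads "Requires inpatient hospitalization or prolongation of an existing hospitalization" and is explained as an overnight stay at least, or a stay longer than expected. The same bullet then lists admissions that do not count. The list opens "Hospital admissions for a surgery planned before study entry, for social" reasons, continues with elective surgery, and ends with normal disease management ("including treatment adjustment) are NOT to be considered as a SAE").

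Section 15.1.1 states: "Definition of an AE includes worsening (in severity and frequency) of pre-existing conditions".

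A later bullet of section 15.1.3 offers a further route. An important medical event "may be considered serious when, based upon appropriate medical judgment, they may jeopardize the patient or subject".

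Under section 15.2.1, "Each adverse event is to be classified by the investigator as serious or non-serious", and that classification sets the reporting route. Section 15.2.2 adds: "All serious adverse events must be reported in an expedited manner to DNDi", within 24 hours of awareness. Section 3.2.2 makes occurrence of a treatment-emergent SAE and time to the first one secondary safety endpoints. Section 16.2.5 bases the narratives on the SAE reports.

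**The concern.** The disease under study is chronic hepatitis C, and section 16.1.3 allows up to half of the population to have compensated cirrhosis. In these subjects, an admission because the liver disease has got worse is also an admission to manage that disease. The exemption does not separate the two, and its mention of treatment adjustment widens it. A site that applies it literally makes no error when it files such an admission as non-serious, and another site may do the opposite.

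The trial is open label with no comparator, so no control group would reveal under-classification; differences between sites would pass straight into the reported SAE proportion. Section 16.2.5 also tabulates safety events by assigned treatment duration. Cirrhotic subjects make up the 24-week group, so any under-classification of this kind would fall mainly on that group and blur the one safety contrast the trial displays.

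**Working it through.** The plan gives no figure to reproduce. The check applies the rules in turn to one case: a subject with compensated cirrhosis is admitted overnight, unplanned, for new ascites that is not life-threatening.

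1. **Is it an AE?** Yes. Cirrhosis was present before the first dose, and section 15.1.1 counts worsening as an AE.
2. **Does it meet the hospitalisation criterion?** Yes. Section 15.1.3 asks for an overnight admission.
3. **Can the exemption remove it?** On a literal reading, yes. The limit to what was planned before study entry is attached to surgery only. Normal disease management carries no such limit, no condition that the subject has not deteriorated, and no definition elsewhere in the protocol. No rule of precedence links the exemption to section 15.1.1.
4. **Do other criteria restore it?** Death, threat to life, incapacity and birth defect do not apply to this case. The important-medical-event criterion could, but it says such events may be considered serious and leaves this to judgment.
5. **Who decides?** The investigator (section 15.2.1).

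The same event therefore has two permitted outcomes:

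| Consequence | Read as worsening | Read as normal management |
|---|---|---|
| AE log (15.2.1) | yes | yes |
| Treatment-emergent SAE count and time to first SAE (3.2.2) | counted | not counted |
| Report within 24 hours (15.2.2) | yes | no |
| Individual narrative (16.2.5) | yes | no |

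The right-hand column assumes that the investigator does not use the discretionary criterion. Section 15.2.1 lists what is captured for every AE. Seriousness and treatment required are on that list; hospital admission is not named as an item.

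**Scale.** The inputs are the overall target of 600 (section 4.1) and the ceiling of 50% with cirrhosis (section 16.1.3): 0.50 × 600 = 300 cirrhotic subjects at most on that target. At that ceiling, each subject whose only SAE is reclassified lowers the SAE proportion among cirrhotic subjects by 1/300 = 0.33 percentage points, and the overall proportion by 1/600 = 0.17 points. The documents give neither an admission rate nor a misclassification rate, so the total cannot be computed.

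**The case against.** The strongest reply is that the exemption has a sensible narrow meaning. The other items on the list are admissions with no new untoward event, and section 15.1.2 follows the same logic in separating a procedure from the condition behind it. The word normal is itself a limit. Section 5.3 excludes anyone with current or past ascites, variceal bleeding or encephalopathy, so new ascites departs from every subject's entry state. This is a fair reading, and a careful investigator may well adopt it. The text does not require it, though, and that is the defect.

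Second, the exemption sits inside one criterion only. Fatal, life-threatening and incapacitating events remain SAEs, and so do those judged medically important. This stands, and it narrows the point. A major variceal bleed, for instance, would probably qualify as life-threatening.

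Third, oversight does not rest on SAEs alone. Grade 3/4 events are analysed separately (sections 3.2.2 and 16.2.5). The CTP score is recorded at each visit from screening in cirrhotic subjects (section 7.2). Related Grade 4 events go to the study team within 24 hours (section 15.3), and in stage 2 a single subject meeting a liver-enzyme stopping criterion prompts a DSMB meeting (section 9.7). Liver-related non-serious AEs are collected through long-term follow-up in stage 2 and in consenting stage 1 subjects (section 15.2.1). This also stands: the event data are not lost. These routes do not restore the SAE endpoints, the expedited report or the narrative.

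A reader might also infer that the cirrhotic schedule steers hepatocellular carcinoma away from SAE status, because footnote 5 of section 7.2 says "any finding of HCC is suspected/confirmed to report as AE". The documents do not support that. By the definition in section 15.1.3 an SAE is an AE, and section 15.2.1 requires seriousness to be classified for every AE. Reporting as an AE starts the seriousness assessment and does not bypass it.

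**Conclusion.** The point holds as a gap in a definition. Section 15.1.3 states a categorical exclusion that, read literally, lets a non-life-threatening, unplanned admission for worsening liver disease be filed as non-serious, and it is not reconciled with section 15.1.1. What is exposed is the treatment-emergent SAE count, time to first SAE, 24-hour reporting and narratives, together with consistency between sites.

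The conclusion assumes that some investigators apply the exemption as written and do not use the discretionary criterion. A reader might go further and infer that a given percentage of cirrhotic subjects would have admissions that vanish from the SAE tables. The documents do not support that: any such percentage would have to be assumed, and so would the misfiling of every admission. The partial backstops make this a modest weakness, but it is cheap to close and concerns the events of most interest in cirrhotic subjects.

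**What to change.** In section 15.1.3, limit the exemption to admissions planned before study entry, or for routine monitoring or treatment of the studied disease, in either case not associated with any deterioration of the subject's condition. Add that an AE, including worsening under section 15.1.1, that requires unplanned admission meets the hospitalisation criterion. Footnote 5 of section 7.2 needs no change.

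This changes reporting only, not treatment. The cost is a short rewording, its submission as an amendment, and a few more expedited reports. The final analysis pools both stages and stage 1 follow-up to week 24 is complete. If stage 1 used the same exemption, the report should say which rule applied to events already classified, or those liver-related AEs should be looked at again.

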15.2. Adverse events reporting

15.2.1. Detecting and documenting AE

The investigator is required to report all directly observed Aes and all Aes reported by the trial subject using concise medical terminology. In addition, at each visit the subjects will be questioned about the occurrence of Aes, with a generic question such as "Since your last visit have you experienced any health problems?"

Stage 1 (for patients who did not consent for long-term follow-up visits): The AE reporting period for this stage of the trial begins upon subject enrolment in the trial (after signature of informed consent for treatment initiation) until 24 weeks' post-treatment completion.

Stage 1 (for patients who consented for long-term follow-up visits) and stage 2: The AE reporting period for this stage of the trial begins upon subject enrolment in the trial (after signature of informed consent for treatment initiation) until:

- End of long-term follow-up visits (SVR 24 + one additional visit for cured patients and 5 additional visits for virological failures): for all serious adverse events.
- End of long-term follow-up visits (SVR 24 + one additional visit for cured patients and 5 additional visits for virological failures): for all liver-related serious and non-serious adverse events.
- 24 weeks' post-treatment completion (SVR 24 visit): for adverse events not associated with any liver-related and not serious.

For both stages of the study:

Serious adverse events will be followed and reported until resolution or stable state.

Information on Aes must be evaluated by a physician. Each adverse event is to be classified by the investigator as serious or non-serious. This classification will determine the reporting procedure for

the event to DNDi and Regulatory Authorities/Ethics Committees (as per local regulatory requirements).

All patients who have Aes, whether considered associated with the use of the investigational product or not, must be monitored to determine the outcome. The clinical course of the AE will be followedup according to accepted standards of medical practice (i.e. until they are resolved or the investigator assesses them as chronic or stable or the subject participation in the trial ends (i.e., until a final report is completed for that subject), even after the end of the period of observation, until a satisfactory explanation is found or the Investigator considers it medically justifiable to terminate follow-up.

All Aes must be recorded in the AE log of the CRF, regardless of apparent causality from use of the study treatment. If known, the diagnosis of the underlying illness or disorder should be recorded, rather than its individual symptoms. If a definitive diagnosis is not possible, the individual symptoms and signs should be recorded. The following information should be captured for all Aes: date, time of onset and end date or outcome (e.g., ongoing), severity of the event, seriousness of the event, Investigator's opinion of the relationship to each investigational product, action taken with regards to each study drug and treatment required for the AE, cause of the event (if known), and information regarding the AE resolution/outcome.

In the CRF, a given AE will be recorded only one time per patient, and the severity recorded will be the maximum level reached. If several distinct episodes of the same condition occur, each episode will be recorded in the CRF.

Serious adverse events should also be reported on the clinical trial AE CRF (in addition to SAE(EAE) form). It should be noted that the form for reporting of SAE (SAE form) is not the same as the AE section of the CRF. Where the same data are collected, the two forms must be completed in a consistent manner, and the same medical terminology should be used.

In addition all medications used to treat the SAE should be documented on the concomitant treatments CRF.

A copy of the submitted SAE form must be retained on file by the Investigator. The Investigator must submit the SAE to the Sponsor and IRB/ IEC and retain documentation of these submissions in the site study file. If the Investigator detects an SAE in a study subject after the end of the period of observation, and considers the event possibly related to prior study treatment, he/she should contact the Sponsor to determine how the event should be documented and reported, and complete a SAE form.

